#### **4. Study Procedures:**

### *Screening:*

Screening for potential candidates for the RCT will be done by the investigators who will run the quality improvement project that started in May 2015: Optimizing Individual Nutrition in Preterm Very Low Birth Weight Infants (STU 102014-045).

Nutrient intake is decided by the clinical care team with recommendations by dietitians, using published data on breast milk composition, published recommendations, weekly rate of growth, feeding tolerance and measurements of serum BUN ( $> 10$  mg/dl), albumin ( $> 3$  g/dl), electrolytes, phosphate and alkaline phosphatase and bone radiograms as needed. Weight and length at birth were previously obtained by nurses and classified using 1963 Lubchenco's growth curve. Size after birth was assessed using the 2003 Fenton's growth curve, length curve including crown-heel measurements (obtained by nurses using paper tape or dietitians using a stadiometer) and height calculated from heel-knee height, mid-arm circumference and abdominal circumference.

New curves have become available on EPIC: weight, length and FOC in 2015 and BMI in 2016. The research team have implemented 2010 Olsen's curve for birth and subsequent measurements up to 39-40 weeks, 2013 Fenton's curves up to 50 weeks PMA, and WHO curves starting at 40-41 weeks), 2015 Holston's (BMI), and serial anthropometric measurements to compare growth parameters with expected values at each stage. Weight gain velocity will be calculated as described by Patel. Linear growth in critical unstable infants will be followed using heel-knee height. BMI will be calculated using only lengths measured on a stadiometer or an infantometer. Nutrition will be optimized using serum BUN goals with adjustment for serum creatinine levels compared to normal values for age. This approach will be standard care, which will be the intervention in any patient entered in the RCT.

### *Randomization:*

Following parental consent, infants will be double blind randomized with 1:1 allocation using a stratified permuted block design by computer, using opaque envelopes in 3 strata: AGA 23-286/7 weeks, SGA 23-286/7 weeks and SGA 29-346/7 weeks. Twins and multiples will be randomized to the same arm of the study.

*Blinding:* Only the dietitian, infant formula technician and a statistician will be aware of the allocation. The other members of the research team, the care givers and the parents will not know the allocation.

### *Study intervention:*

Patients will be randomized to either

- (1) Optimized and individualized nutrition by adjusting milk fortification based on daily measurements of macronutrients in mother's own milk or information on milk from the milk bank
- (2) Or optimized (standard of care at Parkland), i.e., assuming macronutrient concentration in human milk based on available literature and summing enteral and intravenous protein intake

*Data collection in the NICU will be identical to that for other patients who are part of the QI protocol submitted to the IRB: STU 102014-045: Optimizing Individual Nutrition in Preterm Very Low Birth Weight Infants.*

*Procedures done for research* during follow up until 3 years of age include:

- skinfold thickness measurements
- Neurodevelopment exam (Bayley III cognitive and language composite scores) for patients who are not enrolled in the NICHD follow-up study (<27 weeks GA)
- (only if parent checks the box on the consent form): half a teaspoon of blood sample; this blood will be kept in the freezer at -80 degrees for 10 years for measurement of cholesterol, fats, and

some blood markers that may indicate a higher risk for development of diabetes or metabolic syndrome.

- (only if parent checks the box on the consent form): whole-body Dexascan to analyze body composition including percentage of fat at 1 and 3 years of age. The radiation dose is approximately 1% of the Annual US Avg. Natural Background.

Due to COVID-19 restrictions, the 18-26 months Adjusted Age Follow-up extended up to one year from the end of the study window.

## **5. Criteria for Inclusion of Subjects:**

Patients born at Parkland Hospital & Health System

Gestational age < 29 weeks or gestational age < 35 weeks and small for gestational age

Maternal plan to breastfeed or to use milk from the milk donor bank From birth to 1 week of life

## **6. Criteria for Exclusion of Subjects:**

Comfort care only

Patients with major congenital abnormalities

Patients who are too unstable for the first 7 days to have an accurate length measurement

## **7. Sources of Research Material:**

- NICU database
- Duncan's database
- Medical records from Parkland NICU on EPIC
- Medical records from the low birth weight clinic (paper records at the clinic or EPIC)

## **8. Recruitment Methods and Consenting Process:**

Potential subjects may be patients of the investigators.

The researchers will check every day whether a baby is born either very preterm (born at less than 29 weeks of gestational age, that is about three months before expected due dates) or small for gestational age (weight less than the majority [90%] of babies born at same gestational age as your baby) and less than 35 weeks of gestational age. They will ask the mother whether she plans to breastfeed her baby or to have her baby receive milk from the donor's milk bank.

Non-English speaking subjects will be consented using informed consent; a Spanish consent will be available.

All research personnel involved in recruitment has been trained in research ethics and is used to openly communicate with families in the NICU.

Privacy will be assured by talking with the parents in a private room or using soft voice.

All research personnel involved in recruitment has been trained in research ethics and is used to openly communicate with families in the NICU.

If parents are not available, the patient will not be eligible for consenting.

Parents will be paid \$40.00 at each research visit at the low birth weight clinic to reimburse them for parking or travel cost. If they stop taking part in this study or are withdrawn by the research team, they will receive payment for only the visits they have completed. For example, if they complete 3 study visits they will be paid \$120.00.

## **9. Potential Risks:**

Possible side effects include feeding intolerance, high BUN and metabolic acidosis.

Excessive fortification of milk can cause feeding intolerance (full stomach, more residuals [milk aspirated by the nurse] in the stomach before next feeding). Nurses check the baby before each feed and inform the doctor about any sign of feeding intolerance; the doctor may decide to adjust the amount of volume of milk and the amount of fortification if necessary.

Excessive protein intake may raise blood urea nitrogen or BUN, and decrease serum bicarbonate concentration. Blood urea nitrogen (BUN), creatinine and serum electrolytes are measured weekly. If a high BUN: creatinine ratio or a low serum bicarbonate concentration is observed the doctor may decide to decrease the amount of protein supplementation.

Being randomized to the standard arm may, in comparison with the other arm, increase the risk of insufficient nutrition, decreased growth and neurodevelopment. If the baby does not grow well enough, the doctor may decide to give more calories; this may cause the baby to gain fat.

Being randomized to individualized nutrition may, in comparison with the other arm, cause excessive weight gain.

If the parent consents to the Dexascan, the additional radiation dose is approximately 1% of the Annual US Avg. Natural Background.

### SpectraStarTM 2500 XL Neonatal Analyzer

Upon submission of the original protocol, this device was considered by the IRB as a non-significant risk device. We believe this device is a non-significant risk device because

1. Measurement of nutrients in human milk has been used in several centers to adjust fortification of human milk for preterm infants, and has been shown in one randomized trial to improve growth without any risk to the infants.
2. Infants randomized to the treatment arm will have growth velocity and BUN and serum electrolytes measured regularly, as is done for standard of care, to make sure that adjustment of human milk fortification is not exceeding needs for each infant.
3. The Institutional Review Board of Baylor College of Medicine and Affiliated Hospitals and the University of Texas Health Science Center at San Antonio have approved a randomized trial that used this device and was conducted at Texas Childrens and San Antonio without an IDE (Hair et al, attached).

Near infrared (NIR) spectrophotometry has been used to analyze material of solid and liquid states uses the wavelength spectrum 1200 to 2400 nm. Commercially available NIR spectrophotometers have been used to

measure carbohydrate, fat and protein content in animal milk (cow, sheep, donkey and goat) and human milk. These analyzers are used routinely to analyze nutrients in donor's milk provided to NICUs for preterm infants.

The SpectraStarTM 2500 XL Neonatal Analyzer is not approved by the FDA. The SpectraStar 2400 Near Infrared Analyzer (Unity Scientific, Columbia, MD, USA) has been validated against reference chemical analysis of protein, carbohydrate and fat (University of Guelph Laboratory Services, Guelph, Canada) in 42 samples (32 morning, 5 evening, 3 hind milk and 2 foremilk samples) of human milk by Sauer and Kim. Using these samples, the authors generated a calibration curve, which was tested against a second set of 10 samples (6 morning, 0 evening, 1 hind milk and 3 foremilk samples) and their reference values. After logistic regression analysis, the validation set had a correlation ( $r^2$ ) of 0.91 for carbohydrates, 0.95 for fat and 0.95 for protein.

Hair et al have used the SpectraStar 2400 to measure fat content on human milk in a randomized trial involving 78 preterm infants with birth weight 750-1250 grams. In this trial, they found that the addition of milk cream based on results of milk nutrients to calculate individualized supplementation improved weight and length velocity. There was no difference in necrotizing enterocolitis, sepsis or death.

Several observational studies have assessed individualized fortification of milk using similar devices using near infrared spectroscopy to measure nutrients in human milk for preterm infants in the NICU. These studies have shown improved growth without side effects.

### Loss of Confidentiality

Any time information is collected; there is a potential risk for loss of confidentiality. Every effort will be made to keep your information confidential; however, this cannot be guaranteed.

### Risks of Blood Drawing

If the parent agrees, the child will have half a teaspoon of blood collected at 3 years of age for the study. Many children at this age have blood drawn for routine care; we will try to obtain the research blood sample at the same time as blood is drawn for clinical care. Risks associated with drawing blood from your child's arm include minimal discomfort and/or bruising. Infection, excess bleeding, clotting, and/or fainting also are possible, although unlikely.

### Other Risks

There may possibly be other side effects that are unknown at this time.

## **10. Subject Safety and Data Monitoring:**

### How will risks be minimized or prevented?

Potential risks and discomforts will be minimized to the greatest extent possible by using procedures such as appropriate training of personnel, monitoring, withdrawal of the subject upon evidence of difficulty or adverse event; referral for treatment, counseling or other necessary follow-up.

Nurses check the baby before each feed and inform the doctor about any sign of feeding intolerance; the doctor may decide to adjust the amount of volume of milk and the amount of fortification if necessary.

Blood urea nitrogen (BUN) and serum electrolytes are measured weekly. If a high BUN (or BUN: creatinine ratio) or a low serum bicarbonate concentration is observed the doctor may decide to decrease the amount of protein supplementation.

Many children at 3 years of age have blood drawn for routine care; we will try to obtain the research blood sample at the same time as blood is drawn for clinical care.

Type of Research Data or Events to be Monitored:

Study accruals

Protocol deviations: errors in allocation to study arm

Protocol violations: error in amount of fortifier or protein supplementation

Unanticipated problems: NEC, death, sepsis

Adverse events: feeding intolerance, high BUN (or high BUN: creatinine ratio), low serum bicarbonate concentration

Methods and Frequency of Analysis:

Method: review of

report from the database entry

yearly results of the control samples analyses

adverse events and unanticipated adverse events      changes  
in risk/benefits

Frequency: meetings every 6 months after report from the database

Data collection form is attached (spreadsheet)

Person(s) Responsible for Data Monitoring:

Internal DSMC:

The randomized trial has an internal data safety monitoring committee, which meets every 6 mon and reviews the accumulated data. The closed portion of the committee, including [name] and [name], MS, has access to all data including blinded data, and reviews any potential chart that may raise concern, and makes recommendations to the full committee to either stop or continue the study. The rest of the committee, including [name], [name], MD and [name], research coordinator, and [name], do not have access to blinded data.

Name of the person responsible for submitting reports of unanticipated problems, adverse events, protocol deviations and protocol violations to the IRB and sponsor: PI

The PI will send the data safety reports to the IRB.

Reporting Unanticipated Problems, Adverse Events, Protocol Deviations and Protocol Violations:

- PI will report adverse events to the IRB immediately
- PI will report safety reports and DSMC reports to the IRB.

Stopping Rules:

1. Specific stopping rules:

- Less than 10 patients recruited in 12 months
- Mortality in enrolled patients significantly higher than in non-enrolled patients ( $P<0.01$ )
- Necrotizing enterocolitis in enrolled patients more frequent than in non-enrolled patients ( $p<0.01$ )

1. Action indicated by the specific stopping rule:

PI will notify the IRB, all research team members and the funding agency.

Procedures and Time Frames for Communicating Outcomes:

An open report of the accrual and demographics will be provided to the DSMC by the research team. A closed report of mortality and necrotizing enterocolitis will be provided to the DSMC by a statistician.

The report of the DSMC will be provided to the PI and to the IRB.

Precautions for Maintaining Data Integrity:

Random selection of data will be checked by the PI and the DSMC for completeness and integrity.

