#### Secondary endpoints (Aim 2):

In the NICU:

- Disproportionate growth (abdominal circumference, subscapular skinfold and BMI greater than their respective 90th percentiles for age) at 36 weeks of PMA or discharge if patient is discharged earlier than 36 weeks PMA
- Body composition analysis using air displacement plethysmography (Pea Pod)
- Blood pressure (systolic and mean, calm or sleeping) at 36 weeks PMA and discharge
- Hypertension, defined as systolic blood pressure >99th percentile for PMA for at least 24 hours while sleeping or calm
- Blood sample for measurements of cholesterol, fats, cystatin C, adipokines and some blood markers that may indicate a higher risk for development of diabetes or metabolic syndrome at discharge or 36 weeks of PMA, whatever comes first;
- Bacterial diversity and ratio of Firmicutes to Bacteroidetes (F:B) in stool samples (1) at 28 days of age and (2) at 36 weeks or discharge if earlier than 36 weeks
- Body composition analysis using air displacement plethysmography (Pea Pod) at 36 weeks of PMA or discharge if patient is discharged earlier than 36 weeks PMA

At the Follow-up Clinic (Thrive Clinic, [name]), a state-of-the-art facility with >95% follow-up rate, at 6, 12, & 36 months chronological age & 18-26 months adjusted age (PNA corrected for prematurity):

- Neurodevelopment (Bayley III) scores (cognitive and language composite) at 18-26 months adjusted age
- Findings suggestive of metabolic syndrome: disproportionate growth (excessive fat mass) and high systolic blood pressure at each visit at 6 months, 1, 2 and 3 years of age
- Serum levels of cholesterol, fats, cystatin C, adipokines and some blood markers that may indicate a higher risk for development of diabetes or metabolic syndrome at 1 and 3 years of age
- Body composition analysis using air displacement plethysmography (Pea Pod) at 6 months of age
- Body composition analysis using Dexascan (Hologic Horizon A) at 1 and 3 years of age □ Relationship between stool bacterial diversity and F:B ratio, growth and obesity Stopping Rules:

- Less than 10 patients recruited in 12 months
- Mortality in enrolled patients significantly higher than in non-enrolled patients ( $P<0.01$ )
- More frequent necrotizing enterocolitis in enrolled patients ( $P<0.01$ )

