#### **14. Biostatistics:**

The primary outcome variable (growth) will be analyzed by intention to treat (i.e., as randomized). Continuous variables including the primary outcome will be analyzed using Student's t-test or analysis of variance and a generalized linear model (to determine the effect of the intervention while taking into account co-variates and confounding variables). Dichotomous variables will be analyzed using chi-square analysis and by estimating relative risk using robust Poisson regression in a generalized estimating equation model. Subgroup analyses will be done to compare the 3 strata (AGA 23-28 weeks, SGA 23-28 weeks and SGA 29-34 weeks) and to compare SGAs due to insufficient calories (e.g., preeclampsia, low placental insertion) vs. constitutionally small neonates (e.g., congenital infection, genetic anomaly, short parents). A probability value  $<0.05$  will be considered statistically significant. Secondary outcome variables will be analyzed according to appropriate statistical techniques.

Sample size analysis: Based on the number of patients delivered at Parkland during the last 10 years, we expect that 342 (1140x3/10) eligible neonates will be delivered over 3 years. We anticipate enrolling half in the study and expect that 2/3 will survive to 36 weeks PMA. Thus we will enroll 150 patients to yield a 100 patients available for the primary outcome and to have 80% power using 2-tailed Student t-test (alpha error 0.025) to detect an increase in weight gain velocity in the NICU by  $2 \text{ g} \times \text{kg}^{-1} \times \text{day}^{-1}$  (standard deviation  $3 \text{ g} \times \text{kg}^{-1} \times \text{day}^{-1}$ ) and 95% power (alpha error 0.001) to detect an increase in length velocity by 0.2 cm per week (standard deviation 0.2 cm per week), taking into account clustering due to twins and multiples. We will have  $>80\%$  power for both outcomes (alpha error 0.05).

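### The only numerical safety stopping rules pool both randomised arms and compare them with an undefined non-enrolled group; no rule compares the arms on death or NEC.

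*Combined protocol and SAP*

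**What the plan says.** Section 10 (Stopping Rules) lists three rules. One concerns accrual. The other two are the safety rules, each at P<0.01: "Mortality in enrolled patients significantly higher than in non-enrolled patients" and "Necrotizing enterocolitis in enrolled patients more frequent than in non-enrolled patients". Section 1 repeats them, but its NEC rule reads only "More frequent necrotizing enterocolitis in enrolled patients" and names no comparator. The test and its sidedness are not stated.

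Enrolled infants are randomised 1:1 (Section 4, Randomization). The second arm is described as "Or optimized (standard of care at Parkland), i.e., assuming macronutrient concentration in human milk based on available literature", so the enrolled group contains both the new strategy and usual care.

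The non-enrolled group is not defined. Section 14 counts eligible births ("we expect that 342 (1140x3/10) eligible neonates will be delivered over 3 years"), but the rules do not refer to that count. Section 6 excludes comfort-care infants, infants with major abnormalities, and "Patients who are too unstable for the first 7 days to have an accurate length measurement". Under Section 8, an infant whose parents are unavailable cannot be consented. The text does not say whether any of these infants belong to the comparator.

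On oversight, Section 10 gives "Frequency: meetings every 6 months after report from the database". The closed part of the DSMC has access to all data, including blinded data, and "makes recommendations to the full committee to either stop or continue the study". A statistician supplies a closed report on mortality and NEC. That report is not stated to be by arm, and no between-arm threshold is given. When a stopping rule is met, the stated action is notification by the investigator.

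**The concern.** A safety rule in a randomised trial should ask whether the intervention raises the risk of death or NEC. These rules ask whether trial infants fare worse than infants outside the trial, and the answer depends partly on who was enrolled. Three problems follow.

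- **Selection.** A healthier or sicker outside group moves the trigger rate even when the intervention has no effect.
- **Dilution.** An excess confined to one arm is averaged with the other arm.
- **No attribution.** The rule gives the same signal whichever arm carries the excess, although Section 9 names possible risks for each arm.

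At stake is whether the only pre-specified thresholds for the two most serious monitored events use the comparison that randomisation makes valid.

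**Working it through.** **Plan's own figures.** Section 14: 1140 × 3/10 = 342 eligible births, and 150 enrolled × 2/3 = 100 evaluable. Both reproduce. With 1:1 allocation, 150 gives 75 per arm, and 342 − 150 = 192 eligible infants not enrolled. (Enrolling exactly half would leave 171.) The plan gives no event rates or power for the stopping rules, so **every rate below is an assumption**.

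**Pooling.** With control risk p, intervention risk p + d and non-enrolled risk q, the written rule estimates (p + p + d)/2 − q = (p − q) + d/2. The by-arm contrast estimates d. Pooling therefore halves the excess exactly only when q = p. Otherwise the selection term p − q adds to it or cancels it.

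**Trigger probabilities.** Exact binomial enumeration of Fisher's test, two-sided P<0.01, excess in the stated direction, one look, multiples treated as independent. The written rule is 150 versus 192; the by-arm rule is 75 versus 75.

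| Control / intervention mortality | Pooled | Non-enrolled | Written rule | By arm |
|---|---|---|---|---|
| 20% / 40% | 30% | 15% | 76% | 48% |
| 20% / 40% | 30% | 20% | 30% | 48% |
| 20% / 40% | 30% | 25% | 5% | 48% |
| 20% / 40% | 30% | 30% | 0.4% | 48% |
| 33% / 50% | 41.5% | 33% | 15% | 27% |
| 33% / 50% | 41.5% | 40% | 0.9% | 27% |
| 20% / 20% | 20% | 20% | 0.4% | 0.3% each way |
| 20% / 20% | 20% | 15% | 8% | 0.3% each way |
| 20% / 20% | 20% | 10% | 48% | 0.3% each way |

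The 33% rows are set near the one third that Section 14 expects not to survive to 36 weeks. With 171 non-enrolled, the second to fourth rows become 28%, 5% and 0.4%.

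**Attribution.** Swap the arms (control 40%, intervention 20%, non-enrolled 20%). The written rule still triggers 30%. By arm, 48% shows a control excess and essentially 0% an intervention excess.

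**One data set.** With 15/75 deaths in one arm and 3/75 in the other, Fisher gives P = 0.0045. The written rule sees 18/150 (12.0%) against, say, 19/192 (9.9%), P = 0.60, and stays silent.

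**Sensitivity when non-enrolled risk equals control risk** (by arm versus written rule):

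| Control / intervention | Full recruitment | Half (37 per arm, 96 non-enrolled) |
|---|---|---|
| Mortality 10% / 20% | 15% vs 10.5% | 4.0% vs 4.3% |
| NEC 5% / 15% | 23% vs 19% | 4.1% vs 6.2% |
| Mortality 20% / 40% | 48% vs 30% | 18% vs 12% |

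**Repeated looks.** Section 3 gives 2 years of recruitment and Section 14 counts 3 years of births, so 6-monthly looks number 4 or 6. With no effect, mortality of 10% to 30% and unadjusted Fisher tests by arm, the chance of a false trigger in either direction is 0.5–0.6% at one look, 0.9–1.5% over 4 and 1.0–1.8% over 6. If about 30% of infants are in pairs sharing an arm, with within-pair correlation 0.5 (both assumed), it is 1.5–2.7% and 1.8–3.3%.

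**The case against.** The strongest reply is that arm-level monitoring already exists. Closed members see everything, meet every six months and may recommend stopping. A statistician knows the allocation (Section 4, Blinding), and a closed report kept apart from the open one is most naturally read as by arm. Discretion without a fixed boundary is a defensible choice in a single-centre trial of 150 infants meant to supply preliminary data. This stands. A reader might infer that nobody would look at the arms, and the documents do not support that. What is missing is a written between-arm criterion and a statement that the report is by arm.

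Second, the by-arm rule buys little sensitivity. This also stands: at half recruitment it is no better for the smaller harms, and for NEC at 5% versus 15% it is slightly worse. A reader might infer that the written rule generally misses harm. It can err either way, and the documents do not settle which. If infants excluded under Section 6 count as non-enrolled, selection would tend to hide harm; a lower-risk outside group would do the reverse.

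Third, the existing comparison is the only numerical check on harm common to both arms. The 48% trigger at 20% in both arms and 10% outside could be a false alarm or a true trial-wide excess. So the documents do not support dropping it.

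Fourth, Section 4 mentions a parallel quality-improvement protocol with identical NICU data collection, which is a plausible comparator. The rules do not refer to it, so the definition is still needed.

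**Conclusion.** The point holds as a gap worth fixing, at the lower end of importance because of the closed DSMC's access and discretion. The written thresholds apply only to a non-randomised contrast with an undefined group. In the 20% versus 40% illustration, the trigger rate runs from 76% to 0.4% on the outside group's risk alone, against a constant 48% by arm.

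That the rules pool the arms, leave the comparator undefined and set no between-arm criterion rests on the text alone. The percentages rest on assumed event rates, Fisher's test, a single look, 192 non-enrolled and no clustering. The claim is about validity: power for small or early harm is low under either rule.

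**What to change.** In the stopping rules of Sections 1 and 10:

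- Add a by-arm rule for mortality and another for NEC: intervention versus control, all infants as randomised, Fisher's exact test, two-sided P<0.01, with the direction reported to the closed DSMC so that an excess in either arm is visible.
- Have the already unblinded statistician compute it, and state that the closed report is by arm.
- Name Fisher as the governing test. Because multiples share an arm, use the robust Poisson estimating-equation model of Section 14, clustered by mother, as a sensitivity check only.
- Keep enrolled versus non-enrolled as a secondary check for harm common to both arms. Define non-enrolled (for example, concurrent eligible infants not enrolled), say that the comparison is not randomised, and supply the missing comparator in the Section 1 NEC rule.
- State that the six-monthly looks are unadjusted. The false-trigger rates above rest on assumed inputs and should not be written into the protocol.

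The cost is a few sentences and one definition. No new staff are needed and, with the non-enrolled group that the rules already require, no new data. The downsides are that power for small or early harms stays low (about 4% at half recruitment for 10% versus 20%), and that the added rule and repeated looks raise the overall false-trigger rate slightly.
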